4.1 General Principles

The statistical evaluation will be performed by using the software package SAS release 9.4 or higher (SAS Institute Inc., Cary, NC, USA).

The analysis will be based on the Global Standard Tables (Version 4.0 or higher) and the Clinical Pharmacology Standards (CLIPS) (Version 1.2 or higher) where appropriate. Compound Standard Tables will be developed.

The validity of participants for allocation to various analysis sets will be assessed in an ongoing manner in blind review meetings and decisions will be documented in the blind review reports prior to unblinding.

A log-normal distribution is assumed for urinary creatinine and albumin, urinary albumin-to-creatinine ratio (UACR), and N-terminal prohormone B-type natriuretic peptide (NT-proBNP). For all other metric variables, a normal distribution is assumed. The distributional assumptions will be investigated and if necessary, nonparametric methods or transformation of the data will be considered.

All variables will be analyzed by descriptive statistical methods. The number of data available, mean, standard deviation (SD), minimum, median, and maximum will be calculated for metric data. The geometric mean, SD and coefficient of variation (CoV) will be provided instead of the arithmetic mean and SD for the variables where log-normal distributions are assumed, as follows:

$$CoV = \sqrt{\exp(SD_{ln}^2) - 1}$$

SD_{ln} being the standard deviation of the log-transformed values. Frequency tables will be generated for categorical data.

The laboratory parameter eGFR will be calculated based on the Chronic Kidney Disease Epidemiology Collaboration (CKD-EPI) formula (Levey et al., 2009) for all analyses specified in this SAP. For patients recruited in Japan, the Japanese formula adjustment will be applied (Horio et al., 2010).

All participants will be analyzed according to the planned treatment group in FAS per the intention-to-treat (ITT) principle. All participants will be analyzed according to the actual treatment in the Safety Analysis Set (SAF). If a participant receives both treatments due to a

bottle error, the treatment actually received for the majority of the time in the study will be used in SAF.

Only adjudicated outcome events will be used for analysis of the primary and secondary efficacy variables (except for sustained decrease in eGFR $\geq 50\%$ relative to baseline over at least 4 weeks and sustained eGFR decline $< 15 \text{ ml/min}/1.73\text{m}^2$ which will be derived from central laboratory measurements and not be adjudicated); Section 6.2.4 specifies how investigator-reported outcomes for these variables will be summarized. Outcome events for exploratory efficacy variables (e.g. non-fatal myocardial infarction, non-fatal stroke, etc.) will not be adjudicated.

The stratified analyses mentioned in this SAP will be conducted in consideration of the randomization stratification factors:

- LVEF: $< 60\%$, $\geq 60\%$
- Pooled region for stratified analyses: randomization will be stratified by country/region, for the analyses individual countries/regions will be combined into pooled regions as follows:
 - Western Europe and Oceania: Australia, Austria, Denmark, Germany, Israel*, Netherlands, New Zealand, United Kingdom
 - Southwestern Europe: Italy, Portugal, Spain
 - Central Europe: Czechia, Hungary, Poland, Slovakia
 - Southeastern Europe: Bulgaria, Greece, Romania, Turkey
 - Northeastern Europe: Finland, Latvia, Lithuania, Russia, Ukraine
 - Asia: China, Hong Kong, India, Japan, Malaysia, South Korea, Taiwan
 - North America: Canada, United States of America
 - Latin America: Argentina, Brazil, Colombia, Mexico

*Although not geographically located in Western Europe or Oceania, Israel has been included in this pooled region.

In case of issues (e.g. model convergence) with using these predefined pooled regions at the final analyses, the pooled regions may be further combined. Any such changes will be described in the CSR.

All participants will be analyzed according to their correct stratification category. In case of a large number of stratification errors ($\geq 5\%$ of all patients in the FAS), the primary analysis will also be repeated based on the stratification category used in the randomization as a sensitivity analysis.

In case a death cannot be clearly adjudicated as CV-related or non-CV related, it will be adjudicated as undetermined death. Undetermined deaths will be handled as non-CV deaths for the analysis, unless otherwise specified. Where applicable, the combined results of non-CV deaths and undetermined death will be displayed along with results for the individual categories.

4.2 Handling of Dropouts

A participant who has been randomized and discontinues study participation prematurely for any reason, either during study treatment or during post-treatment follow-up, is defined as a ‘dropout’, even if no study drug has been taken. Dropouts will not be replaced.

Data from participants who prematurely terminated the study will be used to the maximum extent possible.

The number of participants discontinuing the epochs, together with the primary reason for discontinuation, will be summarized as described in Section 6.1.1.

The number of participants who prematurely discontinue the study and / or study treatment for any reason, as well as the reasons for premature discontinuation of study and / or study treatment, will be reported. Kaplan-Meier plots for “patients still participating in study” and “patients still on study treatment” will be provided.

All dropouts and participants prematurely discontinuing study treatment will be evaluated with respect to

- baseline characteristics
- potential differences between the treatment groups in the proportion of participant withdrawals or in the timing of withdrawals
- the reasons for premature discontinuation of study and/or study treatment.

4.3 Handling of Missing Data

All missing or partial data will be presented in the subject data listing as they are recorded on the eCRF.

General Rules

When appropriate, the following rules will be implemented so as not to exclude participants or observations from statistical analyses due to missing or incomplete data.

Concomitant medications with missing start and stop date but flagged as being ongoing at a participant’s final visit will be considered to have started prior to study medication start and ended after stopping of study medication. The start and end reference period will be imputed as “before” for the medication start and as “during/after” for the medication end.

In case of partially missing dates for interruptions or permanent stop of study medication intake, a ‘worst-case’ approach will be applied to impute the start and end dates of study medication intake as the earliest and latest possible dates, i.e.:

- first month of the year and/or first day of the month for a partially missing start date, and
- last month of the year and/or last day of the month for a partially missing end date.

If a participant died earlier than the imputed worst study medication end date, the death date will be taken as the study medication end date. However, if these imputations lead to a temporal overlap between different exposure date records, the imputed dates will be adjusted so that no overlap exists and the time on the higher dose is maximized. The date of first exposure to treatment is not expected to be missing as the patients are instructed by the investigator to take their first dose of study drug directly at Visit 1, but in the very rare case

that this date is not recorded, it will be imputed according to the rules outlined above for missing start dates, but not earlier than the randomization date.

When only partial dates are available for clinical events in the efficacy analysis, a median imputation rule will be used:

- For example if the day is missing and the month is July, then day 16 is chosen.
- If the number of potential values is even, the lower of the 2 middle numbers is taken. For example, if the day is missing and the month is June, then day 15 is imputed. The same rule applies if the day and month are missing, e.g. if the year is 2017 and the day and month are missing, 2nd July is used.
- In case the range of possible values is further restricted, e.g. because a patient is randomized in the month in which the day is missing or the participant died in the month in which the day is missing, the median in the restricted set of possible values is calculated. For example, if the clinical event occurred in June 2017 and the respective patient died on 11th June 2017, 6th June 2017 is imputed as the date of the clinical event.

In case a death date is completely missing, it will be imputed on the basis of the last known contact when the participant was still alive and the first known contact when the participant was dead (e.g. from the participant health status follow-up page) as the median of these two dates. As above, if the number of potential values is even, the lower of the two middle numbers is taken.

In case both a non-fatal clinical event and death have partially missing dates, then death takes precedence and will be imputed first according to the rules outlined above. This also applies for non-CV death.

However, given the importance of an accurate determination of the adjudicated event date in relation to randomization date for the time to event analysis, we would expect a minimal number of such missing dates.

A worst-case approach will be applied for determining whether an adverse event (AE) with partially missing dates is treatment-emergent or not, i.e. if it is possible that the AE start date is within a period of study drug intake +3 days (on or after study treatment start date and on or before study treatment end date + 3 days) then the AE is considered treatment-emergent.

If intensity of the AE is missing, the event will be considered as severe. If the drug relationship is missing, the event will be considered as being related to the study drug.

4.4 Interim Analyses and Data Monitoring

One non-binding interim analysis for futility is planned when approximately 30% (~710) of the required total number of primary endpoint events have been observed. If the observed rate ratio (RR) on the primary endpoint is above 0.95, the trial is planned to be stopped for futility. This gives a probability of approximately 69% to stop under the null hypothesis (i.e. no treatment effect on the composite of HHFs and CV deaths) and leads to a loss in power of less than 1% under the alternative hypothesis of the treatment effect assumed for the sample size determination. No adjustment for this loss in power will be made.

The futility analysis given above is considered to be non-binding, the DMC will be asked to also consider important secondary efficacy endpoints as well as safety in their assessment.

In addition, one formal interim analysis for efficacy is planned when approximately 2/3 (~1580) of the required total number of primary endpoint events have been observed.

If the interim analysis shows clear and consistent benefit in the finerenone treatment group, the DMC may recommend early study termination. The Haybittle-Peto rule will be used to guide the decision regarding early stopping of the study for success: a reduction of 3 standard deviations (of the test statistic) in the analysis of the primary efficacy endpoint (two-sided p-value <0.0027) at the interim analysis. In addition, a nominal significant effect on the CV death component should be present (two-sided p-value<0.05) at the interim analysis. Note: The criterion for CV death would not be considered to prove formal statistical significance, as it does not keep the alpha level. It has been added so that the trial is only stopped at the interim if there is at least a certain amount of evidence of a beneficial treatment effect on CV death.

See Section 4.7 for a detailed description of the testing procedure, including an adjustment of the significance level for the interim analysis.

If the study is stopped early, the primary analysis reported in the CSR will consider all events up to the participants' respective EoS visits as would have been the case if the study had not stopped early. A sensitivity analysis will take all events up to the interim analysis datacut date into consideration. For this sensitivity analysis, censoring dates after the datacut date will be reset to the datacut date.

A detailed plan for the routine DMC safety analyses and the interim analysis will be covered in the DMC charter, the analysis planned to be provided to the DMC will be described in a separate SAP with Tables, Listings and Figures (TLFs) attached to the DMC charter. The DMC will review the data in an unblinded manner, both for the routine safety tables and the interim analysis. There are no predefined stopping conditions for the ongoing safety monitoring of this trial. The statistical analysis for the DMC meetings will be performed by an independent statistical analysis center. The sponsor will oversee and discuss with the Steering Committee overall blinded event rates to ensure that they are in line with protocol assumptions. If overall event rates are lower than expected, consideration will be given to altering the study design, such as increasing the sample size or extending the study duration without knowledge of any treatment effect.

4.5 Data Rules

General data rules are described in this section, further data rules for specific parameters or analyses are specified in the respective subsections of Section 6.

4.5.1 Baseline Values

Baseline values will be defined as the last non-missing measurement before or on the day of randomization. If the last observation available prior to randomization is the measurement from the Screening Visit, this would be used as the baseline value. This also includes assessments from a local laboratory, if no assessment from the central laboratory prior to first intake of study drug is available. Otherwise baseline will be missing.

If more than one measurement was planned for a scheduled time point, for example blood pressure (BP) measurements and heart rate, the mean value of the last set of measurements per time point prior to randomization will be used as the baseline value. In case of repeated measurements for pre-treatment visits and Visit 1 (Day 1; baseline), the closest measurement prior to the randomization will be used for analysis instead of the scheduled measurements.

When the Screening and Baseline visits are performed on the same day for a participant, the following assessments (scheduled to be performed at both the Screening and Baseline visits) will only be performed once and the data will appear under Screening:

- NYHA class
- Vital signs
- Local lab potassium and creatinine
- Pregnancy test

Where necessary, these data will be considered in the derivation of baseline values per the rules above.

4.5.2 Change from Baseline

Change from baseline will in general be displayed as absolute change from baseline defined as the difference to baseline, i.e.:

$$\text{Absolute change} = \text{Post baseline value} - \text{baseline value}.$$

Some parameters will be additionally analyzed as relative change defined as

$$\text{Relative change} = 100 * [(\text{post baseline value} - \text{baseline value}) / \text{baseline value}].$$

For specific analyses, the relative decrease of a variable will be analyzed instead of the relative change. The relative decrease is equivalent to the negative of the relative change and defined as

$$\text{Relative decrease} = 100 * [(\text{baseline value} - \text{post baseline value}) / \text{baseline value}].$$

4.5.3 Time Window for Efficacy Events

Events for time to first / recurrent analyses (e.g. primary efficacy endpoint) will be counted from the day of randomization (planned at Visit 1) onwards until the EoS visit following the study termination decision, or until the date of EoS notification + 4 weeks, if the EoS visit has not been performed. In the event of premature discontinuation from the study with no subsequent follow-up information, events will be counted up to the day of the last visit when information on the component is available.

4.5.4 Annual Rate of Recurrent Events

The annual rate of a recurrent event for an individual patient is calculated as:

$$\text{Annual rate} = (\text{Total number of events}) / (\text{Follow-up time (days)} / 365.25)$$

4.5.5 Other Data Handling

Only the data provided by the central laboratory will be used for analysis; values from local laboratories will not be used in the statistical analysis unless otherwise specified and will be listed only. For example, as described above, local values will be used in the derivation of baseline, if no central measurement is available (cf. Section 4.5.1).

At all visits post-randomization and if not stated otherwise, only the values at scheduled measurements will be used for analysis.

For the derived visit “Any time post baseline” (applicable for efficacy) this will include any measurement after randomization, including unscheduled assessments. For the derived visit

“Any time on treatment” (applicable for efficacy), only assessments on or after study medication start date until 30 days after last study drug administration, including unscheduled assessments, will be considered. For safety, “Any time treatment-emergent” will include measurements on or after study medication start date until 3 days after last study drug administration, including unscheduled assessments.

For values which are < LLOQ (Lower limit of quantification), half the value of the LLOQ will be used for analysis. Differences between two values < LLOQ will be assigned values of 0. Ratios between two values < LLOQ will be assigned a value of 1. For values which are > ULOQ (Upper limit of quantification), the ULOQ will be used for analysis.

In case of non-normally distributed data, descriptive statistics other than minimum, maximum and median will only be calculated if at least 2/3 of the individual data were measured and were above the lower limit of quantification. In tables showing descriptive statistics, where values below LLOQ are included, these descriptive statistics will be marked.

4.5.6 Subgroup Analyses

Exploratory subgroup analysis will be done for the primary and secondary efficacy variables. The subgroup analyses will include subgroups based on the stratification factors. The list of key subgroups (in addition to the stratification factors) and other subgroups analyzed is specified below. Analysis will include descriptive statistics, graphical display of estimated treatment effects with 95% confidence intervals (CIs) in a forest plot and a statistical test for interaction.

Subgroups based on stratification factors

- Pooled region for subgroup analysis (Western Europe, Oceania and Others; Eastern Europe; Asia; North America; Latin America); the subgroup Western Europe, Oceania and Others combines the groups Western Europe and Oceania and Southwestern Europe from the pooled region for stratified analyses. The subgroup Eastern Europe combines the groups Central Europe, Southeastern Europe, and Northeastern Europe from the pooled region for stratified analyses.
- LVEF (<60%, \geq 60%)

Key subgroups

- Baseline serum potassium value (\leq 4.5, $>$ 4.5 mmol/L)
- eGFR category at baseline (eGFR $<$ 60, \geq 60 mL/min/1.73 m²)
- Atrial fibrillation at baseline electrocardiogram (ECG) (present, absent)
- Diabetes Mellitus at baseline (present, absent)
- Index HF event (very recent (\leq 7 days before randomization), recent ($>$ 7 days – \leq 3 months), $>$ 3 months or no index HF event).

Other subgroups

- Race (white, black, Asian, other)
- Sex (male, female)
- Age (\leq median vs. $>$ median)
- Baseline body mass index (BMI) ($<$ 30 vs. \geq 30 kg/m²)

- Systolic blood pressure (SBP) at baseline (\leq median vs. $>$ median)
- Angiotensin-converting enzyme inhibitor (ACEI), angiotensin receptor blocker (ARB) or angiotensin receptor-neprilysin inhibitor (ARNI) use at baseline (yes, no)
- Treatment with sodium-glucose transport proteins-2 inhibitor (SGLT-2i) (yes, no)
- NYHA functional class at baseline (II, III/IV)
- Baseline NT-proBNP (\leq median vs. $>$ median)
- Baseline UACR (<30 vs. ≥ 30 mg/g)

For subgroups split by median, the FAS will be taken as reference population for derivation of median.

Individual country analyses, e.g. for Japan, required for regulatory purposes, will be included in a country-specific study SAP.

4.6 Blind Review

The results of the final data assessment will be documented in the final list of important deviations, validity findings and assignment to analysis set(s). Any changes to the statistical analysis prompted by the results of the review of study data will be documented in an amendment and, if applicable, in a supplement to this SAP.

4.7 Testing Procedure and Multiplicity Adjustment

If the interim analysis shows clear and consistent benefit in the finerenone treatment group (defined as two-sided p-value <0.0027 for the primary efficacy endpoint and two-sided p-value <0.05 for the CV death component at the formal interim analysis for efficacy) the DMC may recommend early stopping of the study for success (see Section 4.4 for full details).

If the study is stopped early for success: the final analysis for the primary endpoint will be performed at an overall two-sided significance level of 0.0027. Additionally, the secondary endpoints of:

- Total (first and recurrent) HF events
- Improvement in NYHA class from Baseline to Month 12
- Change from baseline to Month 6, 9 and 12 in TSS from KCCQ
- Time to first occurrence of composite renal endpoint

will be formally tested. The testing strategy of the secondary endpoints is as follows:

1. Total HF events will be tested at the 0.0027 two-sided significance level.
2. If the hypothesis of the secondary endpoint total HF events is rejected, the NYHA class and KCCQ endpoints will be tested using the Bonferroni-Holm procedure, i.e. if at least one of the hypotheses of the two endpoints NYHA class and KCCQ can be rejected at the two-sided (0.0027/2) significance level, the remaining of the two endpoints will be tested at the 0.0027 significance level.
3. If the hypotheses for all previous secondary endpoints are rejected, the composite renal endpoint will be tested at the 0.0027 significance level.

If the test for any endpoint produces a non-significant result, the testing of the remaining endpoints further down in the procedure will be performed in an explorative manner only.

Furthermore, the second component of the primary endpoint (CV deaths) will be tested at the 0.0027 two-sided significance level outside of the alpha-preserving procedure for the primary and other secondary efficacy endpoints (Total HF events, NYHA class, KCCQ, renal composite).

If the study is not stopped early for success: a group sequential design with a single interim analysis when 2/3 of the information is available with a stopping rule of two-sided $p < 0.00270$ would require a small adjustment to the alpha level at the final analysis to maintain the overall significance level at 0.05. For an information fraction of 2/3, the adjusted alpha level of 0.04967 applies. If the study is not stopped early for success a p -value of $p < 0.04967$ is therefore required at the final analysis to achieve formal statistical significance.

If the primary hypothesis is rejected, the secondary endpoints of:

- Total (first and recurrent) HF events
- Improvement in NYHA class from Baseline to Month 12
- Change from baseline to Month 6, 9 and 12 in TSS from KCCQ
- Time to first occurrence of composite renal endpoint

will be formally tested with the following test strategy:

1. Total HF events will be tested at the 0.04967 two-sided significance level.
2. If the hypothesis of the secondary endpoint total HF events is rejected, the NYHA class and KCCQ endpoints will be tested using the Bonferroni-Holm procedure, i.e. if at least one of the hypotheses of the two endpoints NYHA class and KCCQ can be rejected at the two-sided (0.04967/2) significance level, the remaining of the two endpoints will be tested at the 0.04967 significance level.
3. If the hypotheses for all previous secondary endpoints are rejected, the composite renal endpoint will be tested at the 0.04967 significance level.

If the primary hypothesis is not rejected, these tests will be performed in an explorative manner only; similarly, if the test for any secondary endpoint produces a non-significant result, the testing of the remaining endpoints further down in the procedure will be performed in an explorative manner only.

Furthermore, if the primary hypothesis is rejected then the second component of the primary endpoint (CV deaths) will also be tested at the 0.04967 two-sided significance level outside of the alpha-preserving procedure for the primary and other secondary efficacy endpoints (total HF events, NYHA class, KCCQ, renal composite).

Regardless of whether the study is stopped early for success: as a hard endpoint and objective indicator of benefit-risk, time to ACM will be tested at a two-sided significance level of 0.05, after the rejection of the primary hypothesis. Testing of time to ACM will thus be done outside of the alpha-preserving procedure for the primary and other secondary efficacy variables (total HF events, NYHA class, KCCQ, renal composite).

5. Analysis Sets

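### If the trial stops early for success, does testing the primary endpoint at 0.0027 on the data to end of study leave the primary result in doubt?

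*SAP*

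**What the plan says.** SAP 4.7 has two branches.

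- **Stopped early for success.** "the final analysis for the primary endpoint will be performed at an overall two-sided significance level of 0.0027". The hierarchy of total HF events, then NYHA class and KCCQ, then the renal composite is tested at the same level. SAP 4.4 fixes the data: "the primary analysis reported in the CSR will consider all events up to the" participants' own EoS visits, the same cut-off as in a trial that runs its full course. It continues: "A sensitivity analysis will take all events up to the interim analysis datacut date into consideration".
- **Not stopped.** The interim look "would require a small adjustment to the alpha level at the final analysis to maintain the overall significance level at 0.05", which gives 0.04967. In this branch the gate is explicit: "If the primary hypothesis is not rejected, these tests will be performed in an explorative manner only".

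The interim comes at about two thirds of the 2375 target events. Stopping needs two-sided p<0.0027 on the primary endpoint and p<0.05 on CV death. Even then it is a recommendation: "the DMC may recommend early stopping of the study for success". Of the second condition SAP 4.4 says: "The criterion for CV death would not be considered to prove formal statistical significance, as it does not keep the alpha level". For all-cause mortality, in either branch, "time to ACM will be tested at a two-sided significance level of 0.05, after the rejection of the primary hypothesis".

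**The concern.** The interim result that justified stopping becomes a sensitivity analysis, and the same 0.0027 hurdle is applied again to a larger data set. Events between the data cut and the EoS visits (the overrun) could move a narrow crossing back over the line. The trial would then have stopped for efficacy without a formal primary result, and the secondary, CV-death and mortality tests would lose their confirmatory standing.

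Three features suggest that the interim crossing was meant to count by itself:

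- The 0.04967 level charges the interim crossing as a rejection.
- Only the CV-death criterion is said not to keep alpha, which hints that the primary criterion does.
- The early-stop branch does not repeat the sentence that gates the secondary tests on the primary hypothesis.

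If the two readings really conflicted, the status of the primary result could be disputed after unblinding.

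**Working it through.** **1. The plan's own figure.** Inputs from SAP 4.7: interim |Z1|>3 (two-sided 0.0027), information fraction 2/3, overall 0.05. With correlation √(2/3) between the looks, solve P(|Z1|>3 or |Z2|>c)=0.05. This gives c=1.9628, a two-sided level of 0.04967, as stated. The derivation does count an interim crossing as a rejection.

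**2. Type I error under the rule as written.** The trial rejects either by stopping, which needs |Z1|>3, and passing again at |Z|>3, or by going on and reaching |Z2|>1.9628. Each route lies inside the event of step 1, so the total cannot exceed 5%. Suppose every crossing stops and is retested. With overrun information 0.70, the one-sided null probability of crossing and then failing is 0.00038, so alpha is 0.0500 − 2×0.00038 = 0.0492. At information 0.90 it is 0.0500 − 2×0.00085 = 0.0483.

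**3. The passages side by side.**

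- SAP 4.4 names the data and SAP 4.7 names the level. Together they define one test.
- The early-stop branch says that a non-significant result for any endpoint makes everything further down exploratory. The parallel sentence in the other branch is limited to secondary endpoints, because the primary is handled separately there. The early-stop wording therefore naturally includes the primary and acts as the gate.
- The mortality test waits for rejection of the primary hypothesis whether or not the study stopped, so rejection is still open after a stop.
- Protocol 9.4.1.2 gates the secondary and CV-death tests on the primary in every case.
- SAP 4.4 presents the Haybittle-Peto rule as a guide to the stopping decision.

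**4. How often the retest would matter.** Inputs from Protocol 9.2: placebo HF rate 0.0182 and CV-death rate 0.005125 per month, non-CV death 0.0016 per month, frailty variance 5, HF rate ratio 0.75, CV-death hazard ratio 0.80, 5% annual discontinuation, 24 months' accrual. The interim is at 2/3 × 2375 ≈ 1583 events, and every trial meeting both criteria stops.

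Simulation A (24,000 trials per scenario, unstratified LWYY) gives rate ratio 0.812, power 89% and 42.0 months for the protocol's design, against a stated 19% reduction, 90% and 42 months. At one month of overrun:

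| Scenario | Stop | Miss 0.0027, of stops | Of all trials |
|---|---|---|---|
| 5500 participants, protocol rates | 29.1% | 202/6,991 = 2.9% | 202/24,000 = 0.8% |
| 6000, rates × 5500/6000 (assumed) | 30.7% | 144/7,373 = 2.0% | 144/24,000 = 0.6% |
| 6000, rates × 0.80 (assumed) | 30.1% | 2.2% | 0.7% |
| 6000, rates × 5500/6000, effects 0.78 and 0.90 | 8.6% | 2.9% | 0.25% |

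The loss is 19 to 24% of stops with interim |Z| from 3.0 to 3.2, 1.2 to 1.9% from 3.2 to 3.5, and 0 of 17,298 at 3.5 or more.

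Simulation B (6,000 trials, 5500 participants, robust Poisson test, 28.2% stopping) extends the overrun:

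| Overrun, months | Miss, of stops | Of all trials |
|---|---|---|
| 1 | 2.5% | 0.7% |
| 2 | 3.6% | 1.0% |
| 3 | 4.5% | 1.3% |
| 6 | 6.5% | 1.8% |

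No stopped trial had p above 0.04967 at any of these overrun lengths.

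**5. Is the branch still open?** In the simulations under the design effect the interim falls at about month 30 to 32. SAP 6.5 gives 14 September 2020 as the trial start, and SAP version 3.0 is dated 20 June 2024, about 45 months later.

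**The case for a change.** The strongest contrary case is that in a group sequential design a boundary crossing is the rejection, and later data refine the estimate without withdrawing it. The 0.04967 level is calibrated on that basis, so retesting gives up alpha already paid for. That is a respectable position, and the derivation in step 1 does fit it. It shows that the interim crossing could have been allowed to stand, but not that the plan lets it stand. A conservative retest is compatible with a final level that assumes a more generous rule. The remark about CV death is evidence only by silence, and the missing gate is supplied by the sentence about any endpoint.

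Two points stand. No sentence spells out what follows if the interim crosses and the later p-value is 0.0027 or more; the reader has to combine SAP 4.4 with 4.7. And one month is not the whole overrun. The four weeks in the documents run from notification to the EoS visit, and the time from data cut to notification is not given, which is why the table runs to six months. The interim analysis SAP and the DMC charter, which are not in the documents reviewed, may say more.

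**Conclusion.** No change is needed. The plan makes a determinate choice between two defensible conventions: the analysis on events to EoS governs, at 0.0027, and the later tests depend on it. Followed as written it gives a sound conclusion. Type I error does not exceed 5%. Under the design effect the price is about 0.6 to 0.8% of all trials at one month of overrun and about 1.8% at six. At one month the loss comes only from crossings with interim |Z| below 3.5, mostly below 3.2. In return, a stopped trial has to hold its result on the same cut-off that a completed trial would use.

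Making the interim data cut confirmatory would reverse a stated choice on which statisticians reasonably differ. It would add to the null rejection rate at most the null probability of stopping, about 0.05% at a correlation of 0.5 between the two statistics. A sentence on what happens when the two analyses disagree, or a note that the branch has lapsed, would only add detail.

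These sizes rest on the frailty model in Protocol 9.2, on every trial that meets both criteria being stopped, and on assumed overrun lengths and assumed lower event rates for 6000 participants. In simulation B the information fraction at two thirds of the events is about 0.79, not 0.667. That raises the correlation between the looks and so does not weaken the bound on type I error. That the interim has already passed is inference, and the conclusion does not depend on it.
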